## 1. OBJECTIVES

The Primary, Secondary, and Exploratory Objectives are shown in tabular format in the following three tables. See [Figure 1](#) for this Phase 1 / 2 Study Diagram.

Formatted: C-Hyperlink

**Table 1: Primary Objectives and Their Endpoints and Category**

Primary Objectives	Endpoints	Category
Phase 1 only: To determine the safety, tolerability, Maximum Tolerable Dose (MTD), and Recommended Phase 2 Dose (RP2D) of DS-1594b in subjects with relapsed/refractory (R/R) Acute Myeloid Leukemia (AML) and Acute Lymphoblastic Leukemia (ALL).	MTD; RP2D; Safety Profile of DS-1594b;	Safety
Phase 2 only (Cohort A): To evaluate the safety, tolerability, and efficacy defined as Complete Remission (CR) and Complete Remission with Partial Hematologic Recovery (CRh) rate of DS-1594b in subjects with R/R AML with Mixed-Lineage Leukemia rearrangement (MLLr).	CR/CRh rate with DS-1594b monotherapy in R/R AML with MLLr; Safety Profile of DS-1594b	Efficacy Safety
Phase 2 only (Cohort B): To evaluate the safety, tolerability, and efficacy defined as CR+CRh rate of DS-1594b in subjects with R/R AML with a Nucleophosmin 1 mutation (NPM1m).	CR/CRh rate with DS-1594b monotherapy in R/R AML with NPM1m; Safety Profile of DS-1594b	Efficacy Safety
Phase 2 only (Cohort C): To evaluate the safety, tolerability, and efficacy defined as CR+CRh rate of DS-1594b in combination with azacitidine and venetoclax in R/R MLLr or R/R NPM1m AML.	CR/CRh rate with DS-1594b monotherapy in R/R AML with MLLr; Safety Profile of DS-1594b in combination with azacitidine and venetoclax	Efficacy Safety
Phase 2 only (Cohort D): To evaluate the safety, tolerability, and efficacy defined as CR+ Complete Remission with Incomplete Hematologic Recovery (CRI) rate of DS-1594b in combination with mini-HCVD in R/R ALL with MLLr.	CR/CRI rate with DS-1594b in combination with mini-HCVD in R/R ALL with MLLr; Safety Profile of DS-1594b in combination with mini-HCVD	Efficacy Safety

Response definitions Section [8.8](#)

Protocol 2020-0946  
20 Aug 2021  
Version 5.0

**Table 2: Secondary Objectives and Their Endpoints and Category**

Secondary Objectives	Endpoints	Category
Phase 1 only: To evaluate the combined complete remission (CR) and CR with partial hematologic recovery (CRh) rate within 3 months of therapy initiation with DS-1594b in subjects with R/R AML or R/R ALL.	CR/CRh rate in Phase 1	Efficacy

Secondary Objectives	Endpoints	Category
Phases 1 and 2: To assess the composite CR (CRc) rate defined as CR + complete remission with incomplete blood count recovery (CRI), morphologic leukemia free survival (MLFS), partial remission (PR), and overall response rate of subjects with R/R AML and R/R ALL treated on single-agent or combinations of DS-1594b.	CRC rate MLFS rate PR rate ORR (CR + CRI + MLFS + PR) rate	Efficacy
Phases 1 and 2: To determine the: 

• duration of response (DOR),

• time to first response, time to best response,

• rate of durable transfusion independence (TI),

• event-free survival (EFS),

• overall survival (OS),

• measurable residual disease (MRD) by multiparameter flow cytometry at first response and best response,

• 4- and 8-week mortality, and

• number of subjects able to proceed to hematopoietic stem cell transplantation (HSCT) without additional AML therapy and median duration to HSCT from the initiation of single-agent or combinations of DS-1594b in subjects with RR AML and R/R ALL

	

• DOR,

• time to first response, time to best response,

• TI rate,

• EFS,

• OS,

• MRD rate by multiparameter flow cytometry at first response and best response,

• 4- and 8-week mortality

• number of subjects able to proceed to HSCT without additional AML therapy and median duration to HSCT from the initiation of single-agent or combinations of DS-1594b in subjects with R/R AML and R/R ALL

	Efficacy
Phases 1 and 2: To characterize single and multiple-dose pharmacokinetics (PK) of DS-1594b and its metabolites	Cmax, Ctrough, Tmax, Tlast, AUClast, AUCltau, AUCinf, Kel, t1/2, CL/F, Vz/F, AR	PK

Secondary Objectives	Endpoints	Category
Phase 1 only: In a subset of subjects, to evaluate the effect of multiple doses of antifungal agents that are strong CYP3A inhibitors on the PK of DS-1594b	Cmax, Ctrough, Tmax, Tlast, AUClast, AUCtau, AUCinf, Kel, t1/2, CL/F, Vz/F	PK
Phases 1 only: In a subset of subjects, to evaluate the relative exposures of DS-1594b when administered with a standard meal compared to fasted conditions	Cmax, Ctrough, Tmax, Tlast, AUClast, AUCtau, AUCinf, Kel, t1/2, CL/F, Vz/F	PK

**Table 3: Exploratory Objectives and Their Endpoints and Category**

Exploratory Objectives	Endpoints	Category
Phases 1 and 2: To investigate correlations of clinical benefit to single-agent or combinations of DS-1594b with a pre- therapy, on-therapy, and progression using an appropriate NGS panel of gene mutations in AML and ALL, routine cytogenetics/karyotyping, fusion panels, immunophenotyping, and fluorescence in situ hybridization (FISH), when applicable.	Not applicable	PD/Biomarker
Phases 1 and 2: To investigate possible relationships between response and non-response to single-agent or combinations of DS-1594b with pretherapy, on-therapy, and progression gene expression signatures (e.g., MEIS1, MEF2c or HOXA).	Not applicable	PD/Biomarker

Exploratory Objectives	Endpoints	Category

Phases 1 and 2:
 
To investigate the characterization of genetic heterogeneity in AML or ALL tumor cell populations that are longitudinally collected, by performing targeted single-cell sequencing using a novel microfluidic approach that barcodes amplified genomic DNA from thousands of individual leukemia cells confined to droplets (single cell sequencing). Targeted single-cell sequencing is able to sensitively identify cells harboring pathogenic mutations during complete remission and uncover complex clonal evolution within AML or ALL tumors that are not observable with bulk sequencing.
	Not applicable	PD/Biomarker

Phases 1 and 2:
 
To identify individual cell populations (AML/ALL blasts, T-cells – both bulk and T-cell subsets and coreceptor/ligand expression, macrophages and their coreceptor/ligands) and how their signaling state in disease relates to clinical outcomes we will perform CyTOF (mass cytometry) using a customized CyTOF panel specifically developed for this study on subjects' bone marrow samples and peripheral blood at diagnosis, remission and relapse and potentially other time-points on study.
	Not applicable	PD/Biomarker

Exploratory Objectives	Endpoints	Category

Phases 1 and 2: To store and/or analyze surplus blood or tissue including bone marrow, if available, for potential future companion diagnostic development or exploratory research into factors that may influence development of AML/ALL and/or response to therapies (where response is defined broadly to include efficacy, tolerability or safety).
	Not applicable	PD/Biomarker

Phases 1 and 2: To assess the relationship between DS-1594b PK and PD biomarker, safety (e.g. QT prolongation) and efficacy endpoints.
	PK parameters vs. PD, AEs, efficacy	PK

## 2. BACKGROUND

### 2.1. Acute Myeloid Leukemia

Acute Myeloid Leukemia (AML) is a hematologic neoplasm characterized by the proliferation of poorly differentiated myeloid progenitor cells. The disease is particularly difficult to treat in older adults who account for the majority of subjects; thus, the 5-year overall survival is only approximately 27% in newly diagnosed AML. In recent years, multiple studies have characterized distinct molecular subgroups of AML, leading to the discovery of certain disease-associated mutations that are now being used to classify disease, dictate prognosis and, in some cases, guide therapy.

Approximately, 30 to 40% of adults with AML fail to achieve CR with 1 or 2 cycles of induction chemotherapy and are deemed primary refractory. The outcome of subjects with AML who are refractory to induction therapy are dismal, with low response rates (CR/CRi = 15 to 25%) to salvage chemotherapy and poor long-term survival, median OS 4-7 months. We have previously reported a dismal median OS of 3.8 months for subjects with AML who are refractory to HiDAC-containing induction therapy (defined as  $\geq 1\text{gm}/\text{m}^2$  cytarabine per dose). Salvage therapy in such subject populations yielded a response rate of 18% and median response duration of 9 months. These results emphasize the need to explore alternate salvage regimens for subjects with relapsed/refractory AML. The development of novel and effective anti-AML agents and/or combinations is crucial to improving the outcome of AML.

### 2.2. Acute Lymphoblastic Leukemia

Acute Lymphoblastic leukemia (ALL) is a malignant transformation and proliferation of lymphoid progenitor cells. The incidence of ALL follows a bimodal distribution, with the first peak occurring in childhood and a second peak occurring around the age of 50^8. The 5-year overall survival is approximately 90% in children and 30% to 40% in adults and elderly subjects. It is known that chromosomal alterations are a hallmark of ALL and include aneuploidy and recurring chromosomal translocations. KMT2A rearrangements occur in about 5% of ALL and confer resistance to standard chemotherapy as well as novel agents including blinatumomab and inotuzumab.

### 2.3. MLL rearrangements and NPM1 mutations in AML and ALL

Two examples of mutations or cytogenetic aberrations are most relevant to our proposed study here:

**The first example** is the mixed-lineage leukemia (MLL) gene, also known as KMT2A, on chromosome 11q23, which is disrupted in a unique group of acute leukemias. Translocations of MLL gene, which are found in approximately 5%-10% of acute leukemia subjects, result in an aggressive subtype of leukemia, with a 5-year survival rate of only approximately 35%. More than 80 different partner genes in these fusions have been described, although the majority of leukemias result from MLL fusions with one of about six common partner genes (AF4, AF9, ENL, AF10, ELL, PTD) and only 9 specific gene fusions account for more than 90% of all aberrant recombinations of the MLL gene. MLL translocations lead to fusion of the N-terminal

fragment of MLL with 1 of the >80 protein partners, resulting in the expression of MLL fusion proteins that enhance proliferation and block hematopoietic differentiation, ultimately driving the development of leukemia. MLL fusion proteins bind to DNA/chromatin and induce leukemic transformation in hematopoietic stem and progenitor cells through transcriptional deregulation of fusion protein target genes. The best studied of the target genes include HOXA genes and their co-factors MEIS1, which have been shown to be important for leukemia development, cell proliferation, and self-renewal. Because of poor subject outcomes, MLL leukemia represents an unmet medical need, necessitating the development of new therapies.

**The second example** is one of the most common recurrent driver mutations in AML: mutation of the nucleophosmin 1 (NPM1) gene, which is seen in approximately 30% of cases. NPM1 mutations most commonly occur in de novo AML and are associated with a normal karyotype. NPM1 mutations are associated with the upregulated expression of HOXA and MEIS1 genes as do the MLL rearrangements. AML with mutated NPM1 is associated with a more favorable prognosis in the newly diagnosed setting; however, this favorable prognostic effect is lost in the presence of concomitant FLT3-ITD mutations, which are seen in 40%-50% of AML with mutated NPM1, or in a relapsed/refractory setting. In addition to FLT3-ITD mutations, mutations in genes regulating DNA methylation, including DNMT3A, IDH1, and IDH2, are also commonly seen in the presence of NPM1 mutations, and these combined mutations are associated with significantly inferior overall survival, emphasizing the need for new therapies.

Menin is a scaffold protein encoded by the multiple endocrine neoplasia type 1 (MEN1) gene. In the nucleus, menin associates with different proteins that activate or repress the transcription of genes involved in multiple cellular processes. Among them, menin interacts with MLL. MLL has 2 fragments, MBM1 and MBM2, located within the 43-amino acid fragment at the N-terminus of MLL. Because this N-terminus of MLL is retained in MLL fusion proteins, the menin-MLL interaction is preserved among wild-type MLL and all MLL fusion proteins. It has been reported that menin protein interaction with MLL fusion proteins, which leads to upregulation of HOXA and MEIS1 gene expressions, is crucial for the development of acute leukemias with MLL rearrangements. Additionally, it has also been reported that menin protein interaction with wild-type MLL proteins, which is suggested to lead to upregulation of HOXA and MEIS1 gene expressions, is crucial for the development of other types of acute leukemias, such as those with NPM1 mutations. The interaction of MLL1 fusion proteins with menin plays an important role to enhance the proliferation and block the differentiation of hematopoietic cells, ultimately leading to acute leukemia. Therefore, inhibition of the menin-MLL interaction is expected to show efficacy against these acute leukemias. Subjects with MLL-r acute leukemia respond poorly to currently available treatments, emphasizing the urgent need to develop more effective therapies directly disrupting the menin-MLL1 complex.

## 2.4. DS-1594b

### 2.4.1. Pharmacodynamics

DS-1594b is the development designation of a novel, potent, orally available small molecule inhibitor of the binding of MLL1 fusion proteins and wild-type MLL1 to menin in development for the treatment of subjects with hematologic malignancies, including subjects with acute

leukemia with MLL1-r and NPM1 mutations. MLL1 is also known as KMT2A (lysine methyltransferase 2A). The nonclinical testing strategy was designed to demonstrate and characterize the mechanism of action of DS-1594b as well as to support the oral dosing regimen planned for the initial clinical studies. Nonclinical primary pharmacodynamic studies supporting development of DS-1594b were designed to provide information on its mechanism of action and potential for efficacy in the treatment of hematological tumors. In vitro studies assessed the effects of DS-1594b on the interaction between menin and MLL1, cellular growth of MV-4-11, MOLM-13, and K-562 cell lines, and expression levels of *MEIS1*, *HOXA9*, and *PBX3* genes in MV-4-11 and MOLM-13 cell lines. In vivo studies in mice evaluated the effects of DS-1594b on antitumor activity against MV-4-11 xenografts.

#### 2.4.2. Safety Pharmacology and Toxicology

The safety pharmacology parameters were assessed in mice (CNS) and in monkeys (cardiovascular and respiratory systems). DS-1594b was administered orally by gavage in all in vivo studies. In addition, the effect of DS-1594b on the hERG potassium channel current was assessed in vitro. DS-1594b has potent activity on the hERG channel with an  $IC_{50}$  value of 0.3  $\mu$ M. In an in vivo cardiovascular study using telemetered male cynomolgus monkeys, QT and QTc intervals were prolonged following a single administration of DS-1594b at  $\geq 20$  mg/kg in a dose dependent manner. Based on the exposure-response (ER) analysis, the plasma concentration of DS-1594a (free form of DS-1594b) to induce QTc interval prolongation by 10 milliseconds was predicted to be around 1000 ng/mL. No effect on any other cardiovascular or respiratory parameters was noted at doses up to 200 mg/kg. In the 28-day repeated dose toxicity study in monkeys, the QTc interval increased on Days 8 and 22 at  $\geq 60$  mg/kg/day; however, no exacerbation of the increased QTc interval was seen on Day 22 compared to that on Day 8. The anticipated human equivalent dose of the 60mg/kg/day dose in monkeys is approximately 19.2 mg/kg/day.

DS-1594b is highly bound to plasma protein (>97%) in all species. No concentration-dependency was observed across species. Cytochrome P450 (CYP) 3A4 is the primary CYP isoform involved in the metabolism of DS-1594b from the results of experiments using human CYP-expressing microsomes and human liver microsomes. DS-1594b did not inhibit CYP1A2 or CYP2B6 ( $IC_{50} > 50$   $\mu$ M). The  $IC_{50}$  values of DS-1594b were 19.6  $\mu$ M for CYP2C8, 48.4  $\mu$ M for CYP2C9, 2.66  $\mu$ M for CYP2C19, and 27.0  $\mu$ M for CYP2D6 without preincubation and comparable to those with preincubation. In addition, DS-1594b induced time-dependent inhibitory effects on CYP3A.

Results from in vitro studies using Caco-2 cell monolayer systems suggested that DS-1594b is a substrate of efflux transporters. In an exploratory PK study after oral dosing of DS-1594b at 3 mg/kg to rats, AUC increase of DS-1594b was observed by oral pretreatment of elacridar at 50 mg/kg, a P-gp inhibitor which partially inhibits BCRP. These observations indicated that DS-1594b is likely transported by P-gp, and BCRP to a lesser extent.

DS-1594b inhibited OATP1B1 ( $IC_{50}$ : 20.5  $\mu$ M), OATP1B3 ( $IC_{50}$ : 32.3  $\mu$ M), OCT1 ( $IC_{50}$ : 0.489  $\mu$ M), OCT2 ( $IC_{50}$ : 12.8  $\mu$ M), MATE1 ( $IC_{50}$ : 2.78  $\mu$ M), MATE2-K ( $IC_{50}$ : 3.12  $\mu$ M), P-gp ( $IC_{50}$ : 1.79  $\mu$ M) and BCRP ( $IC_{50}$ : 1.94  $\mu$ M) to different extent.

#### 2.4.3. Benefit/Risk Assessment

DS-1594b is under development for the treatment of hematologic malignancies, including acute leukemias with MLL1-r or NPM1-mutations. No clinical studies have been conducted and therefore, no efficacy or safety in humans has been demonstrated.

Nonclinical studies have demonstrated the potent antitumor activity of DS-1594b in mouse models of acute leukemia with MLL1-r or NPM1-mutations. Therefore, DS-1594b is expected to demonstrate efficacy in subjects with MLL1-r or NPM1-mutated acute myeloid leukemia and acute lymphoid leukemia.

Potential risks of DS-1594b, based either on mechanism of action (i.e. differentiation syndrome), or nonclinical toxicity studies or clinical studies with other products of the same class include QT interval prolongation, gastrointestinal toxicity (i.e., nausea, vomiting), hematological (i.e., anemia, neutropenia, and thrombocytopenia), renal, hepatic, skeletal muscle, pulmonary, and cardiac toxicities should be surveilled and appropriately managed in clinical studies.

Based on the nonclinical data, the benefit-risk balance supports clinical development of DS-1594b.

Please see the Investigator Brochure for more information about DS-1594b.

### 3. STUDY DESIGN

This will be a Phase 1/2 study of orally administered single agent DS-1594b in subjects with R/R AML or ALL, including subjects with or without MLLr or NPM1m ([Figure 1](#)[Figure 1](#)).

[figure not shown]
Formatted: C-Hyperlink

The Phase 1 portion of the study is open-label, non-randomized, sequential, B0IN escalation. Dose Escalation will provide the MTD and/or RP2D for the Phase 2 portion and will include two sub-studies to evaluate the drug-drug interaction potential with strong inhibitors of CYP3A and the effect of DS-1594b co-administration with food.

The Phase 2 portion is a four-cohort, open-label, non-randomized study with no crossover permitted between the cohorts to evaluate single agent DS-1594b and combinations of DS-1594b with azacitidine and venetoclax in AML subjects with MLLr or NPM1m, and with mini-HCVD in ALL subjects with MLLr.

A Safety Review Committee (SRC), comprised of selected Sponsor study team members and Investigators, will be responsible for overseeing the safety of dose escalation/de-escalation, declaring the RP2D, and recommending whether to open each expansion cohort. The SRC will review the emerging safety and PK data (if available) from each cohort to determine if dose escalation will occur.

**Figure 1: Study Schema**

Note: All dose levels after the starting dose are tentative. Alternative doses or dosing regimens may be enrolled based on emerging clinical data, including further de-escalation. BID and QD cohorts can be enrolled in parallel and will be evaluated independently for DLT. Cohorts A and B (single agent cohorts) will enroll a maximum of 26 subjects, and Cohorts C and D (combination cohorts) will enroll a maximum of 32 subjects

### 3.1. Rationale for dose and regimen selection

The selection of the starting dose level and regimen is based on the extrapolation of data from cell line efficacy models and toxicology studies in rodents and monkeys.

The DS-1594b Severely Toxic Dose in 10% of animals (STD10) in mice was greater than 300 mg/kg/day and the Highest Non-Severely Toxic Dose (HNSTD) in monkeys was 60 mg/kg/day. The human equivalent dose (HED) of 300 mg/kg/day in mice, based on allometric scaling by body surface area, is approximately 24.3 mg/kg, and using 1/10th of the HED gives a dose of 2.4 mg/kg as the recommended starting human dose for the proposed clinical study. The value of 2.4 mg/kg is lower than a starting dose (3.2 mg/kg) derived from 1/6th of the HED for the HNSTD (60 mg/kg/day) in monkeys. The estimated human systemic exposure at the starting dose exceeds the IC50 of DS-1594b against MV-4-11 human AML cell line (1.97 nM [1.13 ng/mL]), and inhibition of cell proliferation is expected. Therefore, the value of 2.4 mg/kg is considered the appropriate starting dose for the proposed clinical study. No supportive data are available at this stage that would suggest body size-based dosing would reduce human inter-subject variability in PK. Thus, based on an average body weight of 60 kg human, the recommended starting human dose is 140 mg/day. A dosing approach with 70 mg given twice a day will be adopted in order to reduce Cmax while maintaining AUC compared to once-daily dosing to mitigate potential QT interval prolongation risk, given the observed QTc interval prolongation signal seen in monkeys (see Section 2.4.2). In addition, the estimated clinical half-life of DS-1594b is ~ 7 to 8 hours, which also supports a twice daily dosing regimen.

Based on emerging clinical data to assess the PK and safety profile of DS-1594b, the frequency of dosing may be adjusted to once daily (QD), if deemed appropriate and supported by safety data. In this case, dose escalation would follow the same rules as the BID schedule. The SRC

may recommend the enrollment of simultaneous QD and BID dosing regimens or may switch from BID dosing to QD dosing.

In case two dosing regimens are enrolling simultaneously, sequentially enrolling subjects will be assigned to either regimen in an alternating method. After at least 3 subjects have completed the dose-limiting toxicity (DLT) evaluation window for a given cohort, all available clinical data (e.g., PK, safety and any other available data) will be assessed by the SRC to determine if a single dosing regimen (i.e., QD or BID) should be selected. If the SRC selects a single dosing regimen, simultaneous enrollment into both regimens will stop and the remaining subjects in dose-escalation will be enrolled in the subsequent dose level for that selected dosing regimen.

### 3.2. Phase 1 Design

The primary objective of Phase 1 is to determine the Maximum Tolerated Dose (MTD) and the Recommended Phase 2 Dose (RP2D) of DS-1594b when administered as a single agent in subjects with relapsed or refractory AML or ALL, including subjects with or without MLLr or NPM1m using a Bayesian optimal interval (BOIN) design to find the MTD.

The BOIN design is implemented in a simple way similar to the traditional 3+3 design but is more flexible and possesses superior operating characteristics that are comparable to those of the more complex model-based designs, such as the continual reassessment method (CRM).

At least 3 subjects must be enrolled at each dose level. If a dose level is found to be safe by the BOIN design we will escalate to the next higher dose level. The SRC can recommend additional enrollment of up to 9 additional subjects per dose level for dose levels that have already been deemed to be safe with the intent to gain additional information on safety, efficacy and PK at different dose levels, and to guide selection of optimal biologically effective RP2D. These additional 9 subjects per dose level will not be considered evaluable for DLTs. It is anticipated that approximately 18 subjects will be added in this Phase 1 expansion.

Although all R/R ALL and R/R AML subjects, irrespective of mutations, will be allowed during the Phase 1 dose-escalation the goal is to treat at least 3 subjects with MLLr or NPM1m are included at dose levels that are anticipated to be biologically active to allow for optimal evaluation of safety and efficacy in the presumed target population to guide selection of the optimal RP2D.

Treatment during Phase 1 dose escalation phase will follow continuous oral administration under a twice-daily schedule or daily schedule on a 28-day dosing cycle.

The first dose cohort will start at 70 mg twice daily, approximately every 12 hours. The target toxicity rate for the MTD is  $\phi = 0.2$  and the maximum sample size for determining the MTD is 42. Each cohort will include a minimum of 3 subjects. The DLT evaluation period will be limited to the first 28 days of dosing. DLTs are defined in Section 3.2.2 and only those DLTs that occur within the first cycle (28 days) will be used for dose finding. As shown in [Figure 2](#), the BOIN design uses the following rule, optimized to minimize the probability of incorrect dose assignment, to guide dose escalation/de-escalation:

Formatted: C-Hyperlink

- if the observed DLT rate at the current dose is 0.157 or less, escalate the dose to the next higher dose level;
- if the observed DLT rate at the current dose is more than 0.238, de-escalate the dose to the next lower dose level;
- otherwise, stay at the current dose.

Evaluation by the abovementioned BOIN rule will be done for each dose level separately based on the cumulative number of DLT evaluable subjects treated in that dose level and regimen (i.e., QD or BID). In case the multiple dosing regimens are initiated simultaneously and parallel enrollment is allowed in the multiple dosing regimens, the evaluation by the BOIN rule for each dose level and regimen would be made separately. DLT observed after intra-patient dose escalation (IPDE) will not be considered in the dose escalation/de-escalation decision (See Section 6.9 for details about IPDE). For the purpose of overdose control, doses  $j$  and higher levels will be eliminated from further examination if  $\Pr(p_j > 0.2 | \text{data}) > 0.95$  and at least 3 subjects have been treated at dose level  $j$ , where  $p_j$  is the true DLT rate of dose level  $j$ ,  $j = 1, \dots, 6$ . This posterior probability is evaluated based on the beta-binomial model  $y_j | p_j \sim \text{binomial}(p_j)$  with  $p_j \sim \text{uniform}(0,1)$ , where  $y_j$  is the number of subjects who experienced DLT at dose level  $j$ . When the lowest dose is eliminated, stop the trial for safety. The probability cutoff 0.95 is chosen to be consistent with the common practice that when the target DLT rate  $\leq 1/6$ , a dose with 2/3 subjects experienced DLT is eliminated. The above dose escalation/de-escalation and elimination rule can be equivalently presented in [Table 4](#), which will be used to conduct the trial.

Formatted: C-Hyperlink

The steps to implement the BOIN design are described as follows:

1. Three subjects in the first cohort are treated at dose level 1 (70 mg twice daily). Each cohort will include a minimum of 3 subjects.
2. To assign a dose to the next cohort of subjects, conduct dose escalation/de-escalation according to the rule displayed in [Table 4](#). When using [Table 4](#), please note the following:
  - a. “Eliminate” means eliminate the current and higher doses from the trial to prevent treating any future subjects at these doses because they are overly toxic.
  - b. When we eliminate a dose, automatically de-escalate the dose to the next lower level. When the lowest dose is eliminated, stop the trial for safety. In this case, no dose should be selected as the MTD.
  - c. If none of the actions (i.e., escalation, de-escalation or elimination) is triggered, treat the new subjects at the current dose.
  - d. If the current dose is the lowest dose and the rule indicates dose de-escalation, treat the new subjects at the lowest dose unless the number of DLTs reaches the elimination boundary, at which point terminate the trial for safety.
  - e. If the current dose is the highest dose and the rule indicates dose escalation, treat the new subjects at the highest dose.

Formatted: C-Hyperlink

Formatted: C-Hyperlink

3. Repeat step 3 until the maximum sample size of 30 is reached or stop the trial if the number of subjects treated at the current dose reaches 9 and the decision according to [Table 4](#) is to stay at the current dose.

Formatted: C-[Hyperlink](#)

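### If BID and QD run in parallel, BOIN decisions are made per regimen but the stopping steps and MTD selection are written for the whole trial, and the two need to be reconciled

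*Combined protocol and SAP*

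**What the plan says.** **Parallel regimens are foreseen.** Section 3.1 says the SRC "may recommend the enrollment of simultaneous QD and BID dosing regimens or may switch from BID dosing to QD dosing", and that for QD "dose escalation would follow the same rules as the BID schedule".

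**Evaluation is per regimen.** Section 3.2 states that with parallel enrollment "the evaluation by the BOIN rule for each dose level and regimen would be made separately". The Table 4 note and Section 9.1 repeat this. The Figure 1 note says "BID and QD cohorts can be enrolled in parallel and will be evaluated independently for DLT", and Section 5.1.1 agrees.

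**Stopping is per trial.**
- Section 3.2, before the numbered steps and again in step 2b: "When the lowest dose is eliminated, stop the trial for safety. In this case, no dose should be selected as the MTD" (the second sentence is in step 2b only).
- Step 2d, on treating at the lowest dose: "unless the number of DLTs reaches the elimination boundary, at which point terminate the trial for safety".
- Step 3: "stop the trial if the number of subjects treated at the current dose reaches 9 and the decision according to" Table 4 is to stay.

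**MTD selection** is described below Figure 2 as one isotonic fit after the trial is complete, with no mention of regimen.

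**The only closure of a single regimen** is in Section 3.1. After at least 3 subjects in a cohort have completed the DLT window, the SRC may choose one regimen, and then "the remaining subjects in dose-escalation will be enrolled in the subsequent dose level for that selected dosing regimen".

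**The concern.** With two ladders open there are two lowest doses and two current doses, and the stopping steps do not say which is meant. Taken at their word, they let a result in one regimen end dose-finding in the other. Two different things are at stake:

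- **Step 3 (convergence).** When one ladder settles at 9 subjects, the other stops wherever it happens to be. An MTD can still be selected, but the unfinished regimen contributes an incomplete sequence.
- **Steps 2b and 2d (safety).** If the lowest dose of one regimen is eliminated, the trial stops. Under step 2b no MTD may be named, even if the other regimen is well tolerated. The MTD is part of the Phase 1 primary objective.

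Table 5 shows neither effect, because it simulates a single ladder.

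**Working it through.** **1. Reproduce the plan's boundaries.** The target is 0.2. The usual BOIN defaults, 0.6 × 0.2 = 0.12 and 1.4 × 0.2 = 0.28, are assumed.

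- Escalation cut-off: ln(0.88/0.80) / ln[(0.2 × 0.88)/(0.12 × 0.80)] = 0.0953/0.6061 = 0.157.
- De-escalation cut-off: ln(0.80/0.72) / ln[(0.28 × 0.80)/(0.2 × 0.72)] = 0.1054/0.4418 = 0.238.

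Both match Section 3.2. With the uniform prior and the 0.95 cut-off, all three rows of Table 4 also come out as printed.

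**2. What triggers the safety stop.** For 2 DLTs in 3 subjects the posterior is Beta(3, 2), and Pr(p > 0.2) = 1 − [4 × 0.2³ × 0.8 + 0.2⁴] = 1 − 0.0272 = 0.973, which exceeds 0.95. Two DLTs in the first three subjects at a regimen's lowest level are therefore enough. The chance is 3p²(1 − p) + p³:

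- p = 0.20 (first level, scenario 1): 0.104
- p = 0.09 (scenario 2): 0.023
- p = 0.02 (scenario 3): 0.001

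**3. Bound from Table 5 alone.** Early stopping for toxicity is 13.2%, 2.3% and 0% in scenarios 1, 2 and 3. For two independent ladders, the literal wording gives no MTD if either stops, 1 − (1 − a)(1 − b). Stopping within each regimen gives no MTD only if both stop, ab. The first formula ignores which ladder stops first.

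| Scenarios | Either stops | Both stop |
|---|---|---|
| 1 and 1 | 24.7% | 1.7% |
| 1 and 2 | 15.2% | 0.3% |
| 1 and 3 | 13.2% | 0% |
| 2 and 2 | 4.6% | 0.05% |

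**4. Simulate the written rule, 30 subjects per regimen.** Cohorts of 3, 20,000 runs, independent ladders, equal accrual. The order of stopping is respected.

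| Scenarios | No MTD, literal | No MTD, per regimen | Other ladder cut off by step 3 |
|---|---|---|---|
| 1 and 1 | 30.7% | 2.9% | 57% |
| 1 and 3 | 17.0% | 0.02% | 76% |
| 2 and 2 | 5.9% | 0.06% | 81% |
| 2 and 3 | 3.0% | 0.01% | 83% |
| 3 and 3 | 0.2% | 0% | 81% |

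The step 3 cut-off is more frequent than the safety stop in every row. The scenario 1 results exceed those in step 3 above because the written cohorts-of-3 rule stops early in about 17.2% of single-ladder runs, against 13.2% in Table 5.

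**5. Simulate with a shared cap of 42.** Alternating cohorts of 3, both ladders open throughout.

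| BID / QD scenario | No MTD, literal | Correct BID MTD, literal vs per regimen |
|---|---|---|
| 3 / 1 | about 17% | 41% vs 53% (loss 12 points) |
| 4 / 1 | about 17% | 27% vs 47% (loss 20 points) |
| 3 or 4 / 2 | about 3% | loss 3 to 11 points |
| 3 / 3, 4 / 4 | 0.3% or less | loss about 2 points |

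The range in the third row reflects coding choices, such as how a stay at the end of a ladder is treated.

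**6. Sensitivity.**
- If the SRC keeps BID after one QD cohort, the loss in correct BID selection is about 6 points with QD at scenario 1 (48.7% vs 54.3% with BID at scenario 3; 45.0% vs 51.4% at scenario 4) and 1 to 2 points with QD at scenario 2. No-MTD falls to about 10% and 2.6%.
- With a total cap of 30, the figure in step 3 of Section 3.2, the loss with QD at scenario 2 is about 1 point (BID scenario 3) or 3 to 4 points (BID scenario 4).

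**The case against.** The strongest reply is that the intent can be recovered. The two regimens are evaluated independently, QD follows the BID rules, and the stopping steps belong to the BOIN rule that is applied regimen by regimen. On that view the trial in those steps means the BOIN sequence concerned, and the SRC, which reviews every recommendation, would apply it so. This reading is plausible, but no section states it. A safety stop should not need interpreting after a boundary has been crossed.

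It is also fair that the largest figures come from extreme pairings: a first-level DLT rate of 20% on QD against 1% or 2% on BID. They also ignore the SRC's power to drop a regimen. Section 3.1 allows QD only if safety data support it. The readable text defines dose level 1 only for BID, and the schema figure is not available, so a six-level QD ladder is an assumption. All of this stands and limits the size.

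Four stronger inferences are tempting, and the documents do not support them:
- **That the plan intends toxicity in one regimen to close the other.** No such intent is stated.
- **That Section 3.1 says the opposite of the stopping steps.** It covers a discretionary SRC choice between regimens, not a boundary being hit.
- **That every stop forbids an MTD.** Only step 2b does; a step 3 stop leads to MTD selection.
- **That QD is known to be the more toxic regimen.** Section 3.1 gives only a Cmax and QT rationale for starting with BID.

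**Conclusion.** The mismatch is real and conditional. It has no effect unless the SRC opens both regimens. If it does, evaluation and stopping use different units, and nothing limits the stops or the MTD selection to one regimen. Followed literally, the commoner consequence is that one ladder's convergence ends the other. The rarer and more serious one is a Phase 1 with no MTD.

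Under independent six-level ladders, equal accrual, a shared cap of 42 and no SRC regimen selection, no-MTD runs from about 0.3% (both at scenario 3), through 3% to 6% (QD at scenario 2; the upper end is the 2-and-2 pair run with 30 per regimen), to about 17% (QD at scenario 1, BID at 3 or 4). The loss in correct BID selection runs from about 0 to 20 points, and is smaller with a cap of 30 or early SRC selection of one regimen. These are illustrations of size, not predictions.

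**What to change.** Before any QD cohort opens, reconcile the stopping and MTD-selection text of Section 3.2 with the Figure 1 note, Section 3.1, the Table 4 note, Section 5.1.1 and Section 9.1:

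1. Use one stated unit for BOIN evaluation, the step 3 convergence stop and MTD selection. Per regimen matches the evaluation already specified.
2. In step 3, settle the maximum sample size. Step 3 says 30 and the opening of Section 3.2 says 42. State also whether the figure is per regimen or in total.
3. For the safety stops (the sentence before the steps, 2b and 2d), the sponsor and SRC should state explicitly whether elimination of one regimen's lowest dose closes that regimen or the whole trial, and what follows for MTD selection. This review does not say which.

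The cost is wording; Table 4 is unchanged. The downside is that more of the planned dose-finding subjects may be used when both regimens stay open. With a shared cap of 42, mean enrollment in the simulations rose from about 24–35 to about 35–41 when all stops were applied within regimen. That is within 42 but above the 30 in step 3, which is why item 2 must be settled at the same time.
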